5.7. Rescue Medications and Supportive Care

5.7.1. Supportive Care Guidelines for Pembrolizumab

Patients should receive appropriate supportive care measures as deemed necessary by the treating investigator. Suggested supportive care measures for the management of AEs with potential immunologic etiology are outlined along with the dose modification guidelines in [Section 5.3.6.3](#), Table 5. Where appropriate, these guidelines include the use of oral or IV treatment with corticosteroids, as well as additional anti-inflammatory agents if symptoms do not improve with administration of corticosteroids. Note that several courses of steroid tapering may be necessary as symptoms may worsen when the steroid dose is decreased. For each disorder, attempts should be made to rule out other causes such as metastatic disease or bacterial or viral infection, which might require additional supportive care. The treatment guidelines are intended to be applied when the investigator determines the events to be related to pembrolizumab.

Note: If after the evaluation of the event, it is determined not to be related to pembrolizumab, the Investigator does not need to follow the treatment guidance. Refer to [Table 5](#) in [Section 5.3.6.3.2](#), for guidelines regarding dose modification and supportive care.

It may be necessary to perform conditional procedures such as bronchoscopy, endoscopy, or skin photography as part of evaluation of the event.

5.8. Diet/Activity/Other Considerations

5.8.1. Meals and Dietary Restrictions Participants should maintain a normal diet unless modifications are required to manage an AE such as diarrhea, nausea, or vomiting.

5.8.2. Contraception

Galinpepimut-S and pembrolizumab may have adverse effects on a fetus in utero. Furthermore, it is not known if pembrolizumab has transient adverse effects on the composition of sperm. Please refer to [Section 6.6](#) for further details.

Participants should be informed that taking the study medication may involve unknown risks to the fetus (unborn baby) if pregnancy were to occur during the study. In order to participate in the study, participants of childbearing potential must adhere to the contraception requirement (from the day of study medication initiation (or 14 days prior to the initiation of study medication for oral contraception) throughout the study period up to 120 days after the last dose of study medication. If there is any question that a participant of childbearing potential will not reliably comply with the requirements for contraception, that participant should not be entered into the study.

5.8.3. Pregnancy

If a participant inadvertently becomes pregnant while on treatment with either pembrolizumab or galinpepimut-S, the participant will be immediately discontinued from

study treatment. The site will contact the participant at least monthly and document the participant's status until the pregnancy has been completed or terminated. The outcome of the pregnancy will be reported to the Sponsor without delay and within 24 hours if the outcome is a serious adverse experience (e.g., death, abortion, congenital anomaly, or other disabling or life-threatening complication to the mother or newborn). The study investigator will make every effort to obtain permission to follow the outcome of the pregnancy and report the condition of the fetus or newborn to the Sponsor.

[figure not shown]

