 - a. CRC: 2 or 3 lines; b. OvC: 1 or 2 lines; c. SCLC: 1 line; d. TNBC: 1 line; and e. AML: 0 lines (allo-SCT-eligible status or patients with relapsed [2nd line] AML not allowed)
6. Patients should have experienced resolution of toxic effect(s) of the most recent prior chemotherapy to Grade 1 or less (except alopecia). If the patient received major surgery or radiation therapy of > 30 Gy, they must have recovered from the toxicity and/or complications from the intervention.
7. Specifically for patients in the AML arm, the following subject subgroups are eligible:
 - a. Frontline (1st line) patients treated with HMAs since their initial AML diagnosis
 - b. Patients who have required cytoreductive therapy with hydroxyurea or leukapheresis at the time of their initial AML diagnosis, and who subsequently seamlessly transitioned to HMA therapy

- c. Subjects who have experienced induction early failure after initial therapy with 1 - 2 cycles of a standard chemotherapy (“7+3” and similar regimens) and subsequently immediately treated with HMAs as long as such patients have achieved PR as their best observable response after 4 cycles of HMA therapy (per European LeukemiaNet [ELN] criteria).
8. AML patients should continue treatment with HMAs as long as they cannot achieve a response deeper than PR after the completion of administration of 4 cycles of HMAs.
9. If female, patient is eligible to participate if she is not pregnant, not breast-feeding, and at least 1 of the following conditions:
 - a. Not a woman of childbearing potential (WOCBP)
 - b. A WOCBP who agrees to follow contraceptive guidance (agree to use an adequate method of contraception) starting 30 days prior to the administration of the first dose of study therapy and continuing through 4 months after the last study treatment. The effect of galinpepimut-S on the fetus is unknown.
10. Male patients of childbearing potential must agree to use an adequate method of contraception, starting with the first dose of study therapy through 4 months following the last study treatment. It is unknown whether galinpepimut-S affects the sperm, or could be transmitted to the patient’s partner during sexual activity.

Informed Consent

11. Patients (or legally acceptable representative if applicable) should provide written informed consent for the trial.
12. Patients should have measurable/demonstrable active malignant disease per below:

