6.4.1.1. Definitions of Adverse Events

An AE is defined as any untoward medical occurrence in a patient enrolled into this study and does not necessarily have to have a causal relationship (association) with this treatment. An AE can therefore be any unfavorable or untoward sign, symptom, disease, syndrome, intercurrent illness, or abnormal laboratory finding that emerges or worsens relative to the patient's pretreatment baseline, whether or not it is considered to be related to the investigational product.

A TEAE is defined as any event not present before exposure to study treatment or any event already present that worsens in either intensity or frequency after exposure to study treatment.

An SAE is any AE at any dose that:

- Results in death
- Is life-threatening
- Requires inpatient hospitalization or prolongation of existing hospitalization
- Results in persistent or significant disability/incapacity
- Is a congenital anomaly/birth defect
- Constitutes an important medical event (i.e., the AE did not meet any of the above serious criteria but based on appropriate medical judgment, may have jeopardized the patient or required medical or surgical intervention to prevent one of the serious outcomes listed in these criteria)

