6.4.1.2. Eliciting and Documenting Adverse Events

Adverse events will be assessed from the time the patient signs the ICF until 30 days after the last study treatment injection. Adverse events collected before injection of study treatment will be reported as pretreatment AEs and those collected after the first injection of GM-CSF and throughout the study will be reported as TEAEs. Serious AEs that occur more than 30 days after the last dose of study treatment need not be reported unless the investigator considers them related to study treatment. Any medical condition that is present at the time that the patient is screened but does not deteriorate should not be reported as an AE. However, if it deteriorates at any time during the study, it should be recorded as an AE.

At every study visit, patients will be asked a standard nonleading question to elicit any medically related changes in their well-being. They will be asked if they have been hospitalized, had any accidents, used any new medications, or changed concomitant medication regimens (both prescription and over-the-counter medications) or therapies. Patients will also be instructed to contact the investigator at any time after beginning study treatment if any signs or symptoms develop.

In addition to patient observations, AEs identified from any study data (e.g., laboratory values), or identified from review of other documents that are relevant to patient safety will be documented on the AE page in the eCRF.

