6.6. Pregnancy in Partners of Male Patients

Sexually active male patients are required to use a medically acceptable form of birth control while receiving study treatment and for a period of 4 months following the last study treatment injection. It is unknown whether galinpepimut-S affects the sperm or could be transmitted to the patient's partner during sexual activity. The effect of galinpepimut-S on the fetus is unknown. If a male patient's partner becomes pregnant, the pregnant partner will be requested to sign a pregnant partner consent form. The pregnancy will be followed-up to determine the outcome (including complications, spontaneous miscarriage, elective termination, normal birth, or congenital abnormality) and status of mother and child. The occurrence of pregnancy and the outcome of any pregnancy in a partner of a patient treated with galinpepimut-S must be reported to SELLAS (via its CRO, Cancer Insight, LLC) and to the pertinent IRB.

Any partner pregnancy that is brought to the site investigator's attention after the patient has completed the study with a timeframe of pregnancy that coincides with the study treatment period or within 4 months following the last study treatment injection or that has an outcome (such as a miscarriage) considered by the site investigator as possibly related to the study treatment must be promptly reported to SELLAS.

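### Section 5.8.3 requires follow-up and outcome reporting of a female patient's pregnancy only if it begins on treatment, although contraception is required for 120 days after the last dose and partner pregnancies in those 4 months are reportable

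*Combined protocol and SAP*

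**What the plan says.** For a female patient, Section 5.8.3 (Pregnancy) reads: "If a participant inadvertently becomes pregnant while on treatment with either pembrolizumab or galinpepimut-S, the participant will be immediately discontinued". Three duties follow from that one condition: contact at least monthly until the pregnancy ends, reporting of the outcome to the sponsor, and an effort to obtain permission to follow the pregnancy.

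The plan treats fetal risk as lasting beyond treatment. Section 5.8.2 states: "Galinpepimut-S and pembrolizumab may have adverse effects on a fetus in utero". It requires contraception "throughout the study period up to 120 days after the last dose of study medication". Inclusion criterion 9b in Section 4.1.1 gives the same period as 4 months: "continuing through 4 months after the last study treatment".

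For male patients, Section 6.6 is broader: "The occurrence of pregnancy and the outcome of any pregnancy in a partner of a patient treated with galinpepimut-S must be reported". A further sentence extends this to partner pregnancies that a site hears of only once the patient has finished the trial, provided the timing fits: "with a timeframe of pregnancy that coincides with the study treatment period or within 4 months following the last study treatment injection".

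The general safety rules also bear on this. Section 6.4.1.1 lists among the SAE criteria: "Is a congenital anomaly/birth defect". Section 6.4.1.2 collects adverse events until 30 days after the last injection and says that later serious events "need not be reported unless the investigator considers them related to study treatment".

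**The concern.** The plan's own contraception period implies a period of possible fetal exposure after the last dose. In that period the partner of a treated man falls under a pregnancy rule and a treated woman does not, although her exposure is the more direct. The plan states, in criterion 9b and in Section 6.6, that the effect of galinpepimut-S on the fetus is not known. A pregnancy conceived soon after treatment is one of the few ways this trial could add information on that question. A site following Section 5.8.3 to the letter would have no duty to report such a pregnancy or follow it to its end. The plan gives no reason for the difference, which looks like an oversight.

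**Working it through.** No statistical figure is involved. The check compares the time windows and then asks whether another provision covers the difference.

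**Windows after the last dose**

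| Provision | Reach after last dose |
|---|---|
| Contraception, Section 5.8.2 | 120 days |
| Contraception, criterion 9b | 4 months |
| Partner pregnancy reporting, Section 6.6 | 4 months |
| Female patient's own pregnancy, Section 5.8.3 | none beyond the end of treatment |

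**Size of the uncovered window.** The plan does not define when a patient stops being on treatment, so three readings are shown:

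- Treatment ends at the last dose: 120 − 0 = 120 days uncovered.
- Treatment includes the last 3-week cycle: 3 × 7 = 21 days, so 120 − 21 = 99 days uncovered.
- Treatment runs to the end-of-treatment visit, which Table 8 places 30 days after the last injection: 120 − 30 = 90 days uncovered, approximately.

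The first reading fits Section 5.8.3 best, because stopping study treatment at once presupposes that dosing is still under way. The third is arguable, because Table 8 has a separate off-treatment column after the end-of-treatment visit. For relapsed patients, though, Section 6.1.5 allows that visit anywhere from 0 to 30 days after the last injection.

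**Other routes by which a post-treatment pregnancy might be reported**

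1. *Cross-reference.* Section 5.8.2 sends the reader to Section 6.6 for further details, but Section 6.6 deals only with partners of male patients.
2. *Adverse events to day 30.* Sections 6.4.1 and 6.4.1.2 make all adverse events reportable regardless of relationship until 30 days after the last injection. A complication or early loss in that time is covered. A pregnancy as such is not defined as an adverse event.
3. *Serious events after day 30.* These are sure to be reported only if judged related (Section 6.4.1.2). Most outcomes of a pregnancy conceived after treatment would fall here.
4. *Longer adverse-event collection.* Section 6.1.5 follows relapsed patients for adverse events with no stated end, and the adverse-event row of Table 8 appears to continue off treatment. If so, non-serious complications may be captured for longer, but the pregnancy itself and a normal outcome still are not.
5. *Events of clinical interest.* Section 6.4.1.8 lists pembrolizumab overdose and a liver-test combination. Pregnancy is not on the list.
6. *Off-treatment imaging.* Section 6.8.3 names pregnancy among the events that end 3-monthly imaging in patients who stopped without progression. It sets no duty to report the pregnancy or its outcome.
7. *SAE telephone call.* Under Section 6.1.4 this takes place 90 days after the last pembrolizumab dose, or 30 days after treatment stops if new anticancer therapy begins, whichever is earlier. Both fall before day 120, and the call concerns serious adverse events.

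None of the seven requires the occurrence of a female patient's post-treatment pregnancy, or a normal outcome, to be reported.

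**The case against.** The case against giving this weight is fair in several respects.

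- A reader might infer that after treatment nothing is reported unless it is serious and related. The documents do not support that for the first 30 days, when adverse events are reportable whatever their cause. The practical relief is limited, because few outcomes of a post-treatment conception would have occurred by then.
- A reader might infer that the plan never considers pregnancy off treatment in women. Section 6.8.3 shows that it does, since pregnancy ends the imaging schedule and sites must therefore recognise it. That stands, but recognising a pregnancy is not the same as reporting it or following it to outcome.
- A reader might infer that a birth defect could go unreported. By definition it is an SAE, and if judged related it stays reportable with no time limit. What is missing is the duty to follow the pregnancy, without which the site may not learn the outcome.
- A reader might infer that women are not told to report a later pregnancy. The consent pages are not available here, so this cannot be checked either way.
- Numbers will be small. Patients unlikely to comply with contraception are not to be entered (Section 5.8.2), those expecting to conceive through 30 days after the last dose are excluded (Section 4.1.2), and the cohorts have advanced, pretreated cancers or AML not eligible for allogeneic transplant. This stands, and it is why the point is minor.

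**Conclusion.** The gap is real but minor. After the last dose, no pregnancy-specific reporting or follow-up rule applies to a female patient for up to 120 days, or about 99 or 90 days if treatment is read to include the last cycle or to run to the end-of-treatment visit. From about day 30, only serious events that the investigator judges related are sure to be reported, allowing for the plan's inconsistent statements on how long adverse events are collected. The pregnancy itself and a normal outcome are not reportable as such at any time after treatment.

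The conclusion rests on the protocol text alone. The documents give no count of women of childbearing potential, so the number of cases cannot be estimated beyond saying that few are expected. Sample size, endpoints and the Go/Stop rules are unaffected.

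**What to change.** In Section 5.8.3, extend the duty to report the occurrence of pregnancy, and to follow it to outcome, to any pregnancy beginning through 120 days after the last dose of either agent. Adapt the Section 6.6 sentence so that pregnancies the site learns of after the patient has completed the study are included. This matters because Section 4.2 ends each patient's study duration at the end-of-treatment visit. Keep immediate discontinuation tied to patients still being dosed.

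Ask about pregnancy at contacts that already exist: the end-of-treatment visit, the SAE call and the 3-monthly off-treatment contacts. At the end-of-treatment visit, also ask female patients to tell the site of any pregnancy up to day 120, since the SAE call falls earlier than that.

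The cost is a few sentences of protocol text and one question at planned contacts, with no new visit or test. The downside is occasional follow-up of a pregnancy beyond study closure, with the patient's permission.

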5.8.4. Nursing Women

It is unknown whether one of the components of the investigational therapy, i.e., pembrolizumab is excreted in human milk. Since many drugs are excreted in human milk, and because of the potential for serious adverse reactions in the nursing infant, participants who are breastfeeding are not eligible for enrollment.

6. Study Assessments and Procedures

All patients must sign and date the informed consent before any study-specific procedures are performed. The study will be discussed with the patient and he or she will have the opportunity to have any questions answered before signing the ICF. The investigator must address all questions raised by the patient. The investigator will also sign the ICF. The patient must also give authorization regarding privacy requirements before any study-related procedures.

Each patient who provides informed consent and meets all of the inclusion criteria and none of the exclusion criteria at Day -3 (Baseline visit) will be enrolled using IWRS and will be assigned a 5-digit number that will be used on patient documentation throughout the study. The first 2 digits of the number will refer to the site code and the last 3 digits will be a patient-specific number at that site. Patient numbers at each site will be assigned in ascending order and numbers will not be omitted or reused.

Refer to Table 8 for the Schedule of Assessments.

Table 8 Schedule of Assessments

Procedures	Screening Period		Open-Label Treatment Period ^a										Safety Follow-up Period			
	Screening	Baseline ^b	Int. 2 WT1-immunizing Inj (Q3 wk)		Subsequent 4 WT1-immunizing Inj (Q3 wk)		Int. 1	Booster Inj Period - A (Q3 wk)		4 Series of Subsequent Intervals (2-4, 5-7, 8-10, and 11-13)		Booster Inj Period – B (Q12 wk)		Final Pembrolizumab Monotherapy Phase	EOT/ET ^c	Off-treatment
Week			0, 3		6, 9, 12, 15		18	21, 24, 27, 30, 33, 36		[39, 42, 45], [51, 54, 57], [63, 66, 69], [75, 78, 81]		48, 60, 72, 84		87, 90, 93, 96, 99, 102, 105, and 108	30 days after last inj.	Every 3 mnths ^c
Day(s)	-28 to -4	-3 ^b	-2	1	-2	1	1	-2	1	1		-2	1	1		
Informed consent	X															
Inclusion/exclusion	X	X														
Tumor tissue ^d	X															

Procedures	Screening Period		Open-Label Treatment Period ^a										Safety Follow-up Period				
	Screening	Baseline ^b	Int. 2 WT1-immunizing Inj (Q3 wk)		Subsequent 4 WT1-immunizing Inj (Q3 wk)		Int. 1	Booster Inj Period - A (Q3 wk)		4 Series of Subsequent Intervals (2-4, 5-7, 8-10, and 11-13)		Booster Inj Period - B (Q12 wk)		Final Pembrolizumab Monotherapy Phase		EOT/ET ^c	Off-treatment
Week			0, 3		6, 9, 12, 15		18	21, 24, 27, 30, 33, 36		[39, 42, 45], [51, 54, 57], [63, 66, 69], [75, 78, 81]		48, 60, 72, 84		87, 90, 93, 96, 99, 102, 105, and 108		30 days after last inj.	Every 3 mnths ^c
Day(s)	-28 to -4	-3 ^b	-2	1	-2	1	1	-2	1	1		-2	1	1			
Demographics ^e	X																
Prior and concomitant medications	X	X	X	X	X	X	X	X	X	X	X	X	X	X	X	X	
Medical and surgical history	X																
Physical examination ^f	X	X															
ECOG	X	X		X		X	X		X	X	X		X	X	X	X	
Vital signs ^g	X	X		X		X	X		X	X	X		X	X	X	X	

Procedures	Screening Period		Open-Label Treatment Period ^a										Safety Follow-up Period			
	Screening	Baseline ^b	Int. 2 WT1-immunizing Inj (Q3 wk)		Subsequent 4 WT1-immunizing Inj (Q3 wk)		Int. 1	Booster Inj Period - A (Q3 wk)		4 Series of Subsequent Intervals (2-4, 5-7, 8-10, and 11-13)		Booster Inj Period - B (Q12 wk)		Final Pembrolizumab Monotherapy Phase	EOT/ET ^c	Off-treatment
Week			0, 3		6, 9, 12, 15		18	21, 24, 27, 30, 33, 36		[39, 42, 45], [51, 54, 57], [63, 66, 69], [75, 78, 81]		48, 60, 72, 84		87, 90, 93, 96, 99, 102, 105, and 108	30 days after last inj.	Every 3 mnths ^c
Day(s)	-28 to -4	-3 ^b	-2	1	-2	1	1	-2	1	1	-2	1	1			
Height	X															
Weight	X	X		X		X	X		X	X		X	X	X	X	
Beta-hCG	X	X														
HIV testing	X															
12-lead ECG	X															
PT, PTT, and INR	X															
Hematology ^h	X			X		X	X		X	X		X	X	X	X	
Serum chemistry ⁱ	X			X		X	X		X	X		X	X	X	X	

Procedures	Screening Period		Open-Label Treatment Period ^a										Safety Follow-up Period			
	Screening	Baseline ^b	Int. 2 WT1-immunizing Inj (Q3 wk)		Subsequent 4 WT1-immunizing Inj (Q3 wk)		Int. 1	Booster Inj Period - A (Q3 wk)		4 Series of Subsequent Intervals (2-4, 5-7, 8-10, and 11-13)		Booster Inj Period - B (Q12 wk)		Final Pembrolizumab Monotherapy Phase	EOT/ET ^c	Off-treatment
Week			0, 3		6, 9, 12, 15		18	21, 24, 27, 30, 33, 36		[39, 42, 45], [51, 54, 57], [63, 66, 69], [75, 78, 81]		48, 60, 72, 84		87, 90, 93, 96, 99, 102, 105, and 108	30 days after last inj.	Every 3 mnths ^c
Day(s)	-28 to -4	-3 ^b	-2	1	-2	1	1	-2	1	1	-2	1	1			
TSH, FT4, and T3 or FT3	X			X		X	X		X	X		X	X	X		
Urine test ^d	X			X		X	X		X	X		X	X	X		
HLA typing ^k	X															
Cytogenetics and molecular analysis ^l	X															
Bone Marrow biopsy ^m	X					X ^w	X		X ^x	X ^y		X ^z		X		

Procedures	Screening Period		Open-Label Treatment Period ^a										Safety Follow-up Period			
	Screening	Baseline ^b	Int. 2 WT1-immunizing Inj (Q3 wk)		Subsequent 4 WT1-immunizing Inj (Q3 wk)		Int. 1	Booster Inj Period - A (Q3 wk)		4 Series of Subsequent Intervals (2-4, 5-7, 8-10, and 11-13)		Booster Inj Period - B (Q12 wk)		Final Pembrolizumab Monotherapy Phase	EOT/ET ^c	Off-treatment
Week			0, 3		6, 9, 12, 15		18	21, 24, 27, 30, 33, 36		[39, 42, 45], [51, 54, 57], [63, 66, 69], [75, 78, 81]		48, 60, 72, 84		87, 90, 93, 96, 99, 102, 105, and 108	30 days after last inj.	Every 3 mnths ^c
Day(s)	-28 to -4	-3 ^b	-2	1	-2	1	1	-2	1	1		-2	1	1		
Multigene MRD analysis ⁿ	X						X		X ^x	X ^y			X ^z		X	
Immunologic Marker assessment ^o		X				X ^w	X		X ^{aa}	X ^y			X ^z		X	
Biopsies of malignant tissue deposit ^p	X						X		X ^x	X ^t			X ^z		X	
CT or MRI ^q	X					X ^w	X		X ^{aa}	X ^{bb}			X ^z		X	

Procedures	Screening Period		Open-Label Treatment Period ^a										Safety Follow-up Period				
	Screening	Baseline ^b	Int. 2 WT1-immunizing Inj (Q3 wk)		Subsequent 4 WT1-immunizing Inj (Q3 wk)		Int. 1	Booster Inj Period - A (Q3 wk)		4 Series of Subsequent Intervals (2-4, 5-7, 8-10, and 11-13)		Booster Inj Period - B (Q12 wk)		Final Pembrolizumab Monotherapy Phase		EOT/ET ^c	Off-treatment
Week			0, 3		6, 9, 12, 15		18	21, 24, 27, 30, 33, 36		[39, 42, 45], [51, 54, 57], [63, 66, 69], [75, 78, 81]		48, 60, 72, 84		87, 90, 93, 96, 99, 102, 105, and 108		30 days after last inj.	Every 3 mnths ^c
Day(s)	-28 to -4	-3 ^b	-2	1	-2	1	1	-2	1	1		-2	1	1			
Enrollment to study ^r		X															
GM-CSF SC ^s			X	X	X	X		X	X			X	X				
Assess local immunization site		X		X		X			X				X				
Galinpepimut-S ^t				X													
Galinpepimut-S with pembrolizumab						X			X				X				

Procedures	Screening Period		Open-Label Treatment Period ^a										Safety Follow-up Period				
	Screening	Baseline ^b	Int. 2 WT1-immunizing Inj (Q3 wk)		Subsequent 4 WT1-immunizing Inj (Q3 wk)		Int. 1	Booster Inj Period - A (Q3 wk)		4 Series of Subsequent Intervals (2-4, 5-7, 8-10, and 11-13)		Booster Inj Period - B (Q12 wk)		Final Pembrolizumab Monotherapy Phase		EOT/ET ^c	Off-treatment
Week			0, 3		6, 9, 12, 15		18	21, 24, 27, 30, 33, 36		[39, 42, 45], [51, 54, 57], [63, 66, 69], [75, 78, 81]		48, 60, 72, 84		87, 90, 93, 96, 99, 102, 105, and 108		30 days after last inj.	Every 3 mnths ^c
Day(s)	-28 to -4	-3 ^b	-2	1	-2	1	1	-2	1	1	-2	1	1				
30-minute post injection observation				X	X	X		X	X			X	X				
Pembrolizumab administration alone							X			X			X	X			
Adverse events ^u	X	X		X	X	X	X	X	X	X	X	X	X	X	X	X	X
Evaluation of survival ^v				X		X	X		X	X		X	X	X	X	X	X

Abbreviations: ECG, electrocardiogram; ECOG, Eastern Cooperative Oncology Group; EOT, end of treatment; GM-CSF, granulocyte-macrophage colony-stimulating factor (sargramostim); INR, international normalized ratio; IV, intravenous; MRI, magnetic resonance imaging; MRD, minimal residual disease; mnths, months; PT, prothrombin time; PTT, partial thromboplastin time.

- a. To assess progression-free survival, relapse must be documented, and the following procedures performed: concomitant medication, AEs, ECOG performance status, blood samples (hematology, serum chemistry, immune/exploratory correlates), and evaluation of clinical endpoints. For AML patients that have relapsed, the relapse visit will also include BM aspiration. For non-progressors: At the time of progression/relapse documentation, an additional 'relapse visit' will be performed; refer to [Section 6.1.5](#).
- b. At the baseline visit (Day -3), all pretreatment screening procedures and assessments must be completed, review of inclusion/exclusion criteria (including specific tumor histologic type verification, [e.g., TNBC]), and review of laboratory and tissue pathology results confirmed prior to enrollment and the first GM-CSF injection.
- c. Patients who complete the study treatment period or patients who discontinue early (if they have received at least 1 treatment injection) will enter an off-treatment follow-up period to assess progression-free survival and overall survival. A follow-up phone call for serious adverse events will occur 90 days after the last dose of pembrolizumab OR 30 days following cessation of study treatment if the patient begins a new anticancer therapy, whichever is earlier. If the patient begins a new anticancer therapy, this must be reported by the investigator. If a patient is confirmed to have recurrent/refractory/relapsed disease after completion of a relapse visit, the patient is to return to the site within 30 days after their last treatment injection to complete EOT/early termination visit procedures.
- d. Retrieval of archival specimens (paraffin block sections) of tumor tissue (for solid tumors) or bone marrow (for AML) for WT1 IHC testing. Biopsy of current tumor tissue (for solid tumors) or bone marrow (for AML) for WT1 IHC. For CRC only: additionally, collection of current tissue sample for microsatellite stability analysis.
- e. Demographics will include sex, age, race and ethnicity.
- f. Abnormal physical examination findings identified at the screening visit will be followed until resolution or stabilization. Any ongoing findings (after study enrollment) should be recorded as pretreatment adverse events (AEs) and will be graded by Common Terminology Criteria for Adverse Events (CTCAE), Version 5.0.

- g. Vital will include body temperature, systolic and diastolic blood pressure, heart rate, and respiratory rate.
- h. The hematology assessment will include a complete blood count (CBC) with differential and platelet count. These samples will be collected for processing by the central laboratory. Samples must be collected before study treatment administration. For abnormal complete blood count results, a manual differential is required. Specifically for AML patients, if the differential is suggestive of abnormal or immature cells and a possible relapse, a bone marrow biopsy must be performed as part of a scheduled relapse visit. See the laboratory manual for more information.
- i. The serum chemistry assessments will include sodium, potassium, chloride, carbon dioxide, blood urea nitrogen, creatinine, calcium, total protein, albumin, glucose, total bilirubin, alkaline phosphatase, aspartate aminotransferase, alanine aminotransferase, and lactate dehydrogenase. These samples will be collected for processing by the central laboratory. Samples must be collected before study treatment administration. Calculated Creatinine Clearance (CrCl) must be assessed during the screening period to determine eligibility. See the laboratory manual for more information.
- j. Urine dipstick testing will be performed locally at the site.
- k. Patients will provide any historical documentation of HLA type at the pretreatment screening visit. The majority of patients will not have such information available and must undergo HLA typing assessment at participating sites.
- l. ***For AML patients ONLY:*** provide historical documentation of cytogenetic and molecular analyses results (from initial diagnosis) at the pretreatment screening visit. Only patients with abnormal karyotype at initial diagnosis will require to repeat karyotype plus/minus fluorescence in situ hybridization (FISH) at pretreatment screening in this study. Full molecular analysis (i.e., FLT3-ITD and NPM1 mutations, etc.) will also be performed on bone marrow biopsy samples collected during pretreatment screening in all AML patients.
- m. ***For AML patients ONLY:*** a bone marrow aspiration and biopsy is required during pretreatment screening to confirm morphologic partial response (PR) or stable disease (SD) status, for MRD analysis, and for cytogenetic and molecular analyses as defined in footnote k. Additional bone marrow biopsies are required as shown per schedule, as well as at the end-of-treatment/early termination visit to evaluate progression and MRD. If a peripheral blood differential result (including manual differentiation) at any study visit is suggestive of abnormal or immature cells and a possible relapse, a bone marrow biopsy must be performed as part of a scheduled AML relapse visit. If the bone marrow biopsy confirms relapse, the patient will be discontinued from the study and will need to return to the site 0 to 30 days after their last treatment injection for end-of-treatment/early termination procedures. The bone marrow aspiration performed as part of the scheduled relapse visit will serve as bone marrow aspiration procedure required at the end-of-treatment/early

termination visit. A bone marrow biopsy must be collected if an adequate aspiration is not attainable. Refer to the laboratory manual for collection and processing these samples.

- ⁿ. ***For AML patients ONLY***: Analysis of MRD will be performed on samples of peripheral blood and will be evaluated by molecular analysis of transcripts. Peripheral blood samples will be collected from patients according to the schedule shown. Samples must be collected before study treatment administration. Refer to the laboratory manual for collection and processing of samples.
- ^o. Peripheral blood samples for immunologic response (IR) assessment will be collected from a large subset of patients enrolled in each of the 5 arms of the study at select sites as per the schedule shown. The study is aiming to analyze IR profile in at least 50% of the enrolled patients. Samples must be collected before study treatment administrations. Refer to the laboratory manual for collection and processing these samples.
- ^p. Biopsies of malignant tissue deposit (or bone marrow, for AML patients) will be performed according to the schedule shown in a subset of patients at select sites. These tissue specimens will be used to study the presence and kinetics of host immunocytes infiltrating the above tissues, as well as the expression of key markers of immune biological significance in the tumor microenvironment. All biopsies are in principle mandatory, as long as the tumor deposits are technically accessible and such biopsies can be conducted safely.
- ^q. For solid tumors only: CT or MRI staging assessment (both per RECIST and iRECIST).
- ^r. Prior to contacting IWRS to enroll a patient into the study and obtaining a patient number, the following must be reviewed and verified: inclusion/exclusion criteria (including specific tumor histologic type verification, [e.g., TNBC]), laboratory and tissue pathology.
- ^s. GM-CSF will be administered 2 days before and on the day of each galinepimut-S administration. A GM-CSF dose of 70 µg will be injected subcutaneously at the same anatomical site as the planned subsequent galinepimut-S injection (to be given during the same cycle of therapy). Before injection, study staff should assess the immunization site. On Day -1, patients will remain in the clinic for approximately 30 minutes following receipt of GM-CSF to monitor for any adverse reactions. Blood samples will be collected before study treatment administration.
- ^t. Immediately after the patient receives the GM-CSF injection, patients are to receive galinepimut-S injected SC in the same anatomical location as the GM-CSF injection. The injection site should be on the arm, leg, or torso of the patient, and should be positioned at least 5 cm away from the previous site of study treatment injection.
- ^u. Adverse event reporting begins from the time of signing the ICF to 30 days after the last injection of any study treatment (GPS/placebo or pembrolizumab). Adverse events collected before the first injection of GM-CSF will be reported as “pre-WT1 AEs”. All AEs will be graded by

CTCAE, Version 5.0. A follow-up phone call for serious adverse events will occur 90 days after the last dose of pembrolizumab or 30 days following cessation of study treatment if the patient begins new anticancer therapy, whichever is earlier. If the patient initiates new anticancer therapy, this must be reported by the investigator.

- v. Patients who complete the study, or who discontinue because of any reason other than recurrent/refractory/relapsed disease will return to the site 30 days after their last injection for final safety follow-up and completion of EOT/ET visit.
- w. Only to occur at Week 9.
- x. Only to occur at Week 36.
- y. Only to occur at Week 54.
- z. Only to occur at Weeks 72 and 84.
- aa. Only to occur at Weeks 27 and 36.
- bb. Only to occur at Weeks 45, 54, and 63.

